APPENDIX C. SENSITIVITY ANALYSIS: 2-DIMENSIONAL TIPPING POINT ANALYSIS

The following represents an outline of the planned methodology for the “2-dimensional tipping point” multiple imputation sensitivity analysis of the change from baseline in weekly average of the percent predicted trough morning FEV₁ at week 12. Minor deviations from this outline will be addressed in the CSR. In the situation that more significant updates are warranted, changes will be addressed in a SAP amendment to be finalized prior to database lock.

The 2-dimensional tipping point analysis evaluates several combinations of imputed missing data values until it reaches a “tipping point” or point at which a particular combination of imputed missing data changes the study conclusions, as summarized by its p-value. This is a sensitivity analysis utilizing MI under the missing not at random (MNAR) assumption, and will be only conducted if a significant result ($p \leq 0.05$) is observed as part of the primary analysis. If the sensitivity analysis reveals that the tipping point consists of unreasonable values, then the robustness of the study results is supported.

Change from Baseline in Weekly Average of the Percent Predicted Trough Morning FEV₁ at Week 12:

In the 2-dimensional tipping point analysis, missing percent predicted FEV₁ values will be imputed for patients who discontinued treatment before the week 12 visit for weekly average in which FEV₁ values are missing. MI and associated combining rules will be applied to propagate imputation uncertainty. In each treatment group, the missing percent predicted FEV₁ values will be imputed based on measurements observed at previous weeks and in the same treatment group. For the active groups, a constant (positive value) shift will be subtracted from the imputed FEV₁ values. For the placebo group, a constant (positive value) shift will be added to the imputed FEV₁ values. The initial shift values will be zero (representing MAR) and they will then be increased and the process repeated until the treatment effect is no longer significant at the 5% level. The shift point at which the effect is no longer significant is the tipping point.

More specifically, the "tipping point" analysis will be performed using the following steps:

1. Assume patients with arbitrary missing data patterns, the fully conditional specification statement will be used to impute by using regression with treatment arm and percent predicted FEV₁ measurements from previous weeks as explanatory variables. For the 3 active treatment groups, MNAR will be assumed using specified shift parameters to adjust imputed values. For the placebo group, first imputed values will be generated using a zero shift parameter (namely, MAR is assumed for placebo). This will be done using code similar to the following:

```
proc mi data= outmi_mono seed=56789 nimpute=10 out=outmi;
  class trt sex therapy center;
  fcs nbiter=50 reg(wk1= &covlist trt / details);
  fcs nbiter=50 reg(wk2= &covlist trt wk1 / details);
  fcs nbiter=50 reg(wk3= &covlist trt wk1 wk2 / details);
```

```
fcs nbiter=50 reg(wk4= &covlist trt wk1 wk2 wk3 / details);
fcs nbiter=50 reg(wk5= &covlist trt wk1 wk2 wk3 wk4 / details);
fcs nbiter=50 reg(wk6= &covlist trt wk1 wk2 wk3
                  wk4 wk5 /details);
fcs nbiter=50 reg(wk7= &covlist trt wk1 wk2 wk3
                  wk4 wk5 wk6 / details);
fcs nbiter=50 reg(wk8= &covlist trt wk1 wk2 wk3
                  wk4 wk5 wk6 wk7 / details);
fcs nbiter=50 reg(wk9= &covlist trt wk1 wk2 wk3
                  wk4 wk5 wk6 wk7 wk8 / details);
fcs nbiter=50 reg(wk10= &covlist trt wk1 wk2 wk3
                  wk4 wk5 wk6 wk7 wk8 wk9 / details);
fcs nbiter=50 reg(wk11= &covlist trt wk1 wk2 wk3
                  wk4 wk5 wk6 wk7 wk8 trt wk9 wk10 / details);
fcs nbiter=50 reg(wk12= &covlist trt wk1 wk2 wk3
                  wk4 wk5 wk6 wk7 wk8 wk9 wk10 wk11 / details);

mnar adjust( wk1 / shift=&sj adjustobs=(trt='A' ));
mnar adjust( wk2 / shift=&sj adjustobs=(trt='A' ));
mnar adjust( wk3 / shift=&sj adjustobs=(trt='A' ));
mnar adjust( wk4 / shift=&sj adjustobs=(trt='A' ));
mnar adjust( wk5 / shift=&sj adjustobs=(trt='A' ));
mnar adjust( wk6 / shift=&sj adjustobs=(trt='A' ));
mnar adjust( wk7 / shift=&sj adjustobs=(trt='A' ));
mnar adjust( wk8 / shift=&sj adjustobs=(trt='A' ));
mnar adjust( wk9 / shift=&sj adjustobs=(trt='A' ));
mnar adjust( wk10 / shift=&sj adjustobs=(trt='A' ));
mnar adjust( wk11 / shift=&sj adjustobs=(trt='A' ));
mnar adjust( wk12 / shift=&sj adjustobs=(trt='A' ));

mnar adjust( wk1 / shift=&sj adjustobs=(trt='B' ));
mnar adjust( wk2 / shift=&sj adjustobs=(trt='B' ));
```

```
mnar adjust( wk3 / shift=&sj adjustobs=(trt='B' ) );
mnar adjust( wk4 / shift=&sj adjustobs=(trt='B' ) );
mnar adjust( wk5 / shift=&sj adjustobs=(trt='B' ) );
mnar adjust( wk6 / shift=&sj adjustobs=(trt='B' ) );
mnar adjust( wk7 / shift=&sj adjustobs=(trt='B' ) );
mnar adjust( wk8 / shift=&sj adjustobs=(trt='B' ) );
mnar adjust( wk9 / shift=&sj adjustobs=(trt='B' ) );
mnar adjust( wk10 / shift=&sj adjustobs=(trt='B' ) );
mnar adjust( wk11 / shift=&sj adjustobs=(trt='B' ) );
mnar adjust( wk12 / shift=&sj adjustobs=(trt='B' ) );

mnar adjust( wk1 / shift=&sj adjustobs=(trt='C' ) );
mnar adjust( wk2 / shift=&sj adjustobs=(trt='C' ) );
mnar adjust( wk3 / shift=&sj adjustobs=(trt='C' ) );
mnar adjust( wk4 / shift=&sj adjustobs=(trt='C' ) );
mnar adjust( wk5 / shift=&sj adjustobs=(trt='C' ) );
mnar adjust( wk6 / shift=&sj adjustobs=(trt='C' ) );
mnar adjust( wk7 / shift=&sj adjustobs=(trt='C' ) );
mnar adjust( wk8 / shift=&sj adjustobs=(trt='C' ) );
mnar adjust( wk9 / shift=&sj adjustobs=(trt='C' ) );
mnar adjust( wk10 / shift=&sj adjustobs=(trt='C' ) );
mnar adjust( wk11 / shift=&sj adjustobs=(trt='C' ) );
mnar adjust( wk12 / shift=&sj adjustobs=(trt='C' ) );

mnar adjust( wk1 / shift=0 adjustobs=(trt='D' ) );
mnar adjust( wk2 / shift=0 adjustobs=(trt='D' ) );
mnar adjust( wk3 / shift=0 adjustobs=(trt='D' ) );
mnar adjust( wk4 / shift=0 adjustobs=(trt='D' ) );
mnar adjust( wk5 / shift=0 adjustobs=(trt='D' ) );
mnar adjust( wk6 / shift=0 adjustobs=(trt='D' ) );
mnar adjust( wk7 / shift=0 adjustobs=(trt='D' ) );
mnar adjust( wk8 / shift=0 adjustobs=(trt='D' ) );
```

```

mnar adjust( wk9 / shift=0  adjustobs=(trt='D' ));
mnar adjust( wk10 / shift=0  adjustobs=(trt='D' ));
mnar adjust( wk11 / shift=0  adjustobs=(trt='D' ));
mnar adjust( wk12 / shift=0  adjustobs=(trt='D' ));

var trt &covlist wk1 - wk12;

run;

where: the order of &covlist includes: sex, (pooled investigational
center, previous therapy, base, and age

Note: wk1 - wk12 is the AVAL raw data, change from baseline values
should not be used in PROC MI procedure.

```

The same shift will be assumed for all weekly average and all treatment groups.

2. The MMRM model will be fitted to the completed datasets using the model that was used for analysis. The difference will be estimated in adjusted LS means and p-value. SAS code similar to the following will be used:

```

ods output diffs=midiffs;
proc mixed data=dataset;
  by shift;
  class usubjid sex center therapy visit trt;
  model chg=base sex age center therapy visit trt visit*trt /
    ddfm=KR alpha=0.05;
  repeated visit / type=un sub=usubjid(trt) r;
    ** repeated visit / type=cs sub=usubjid(trt) r;
    ** if type=un fails to converge;
  lsmeans trt / diff cl;
run;

```

3. The results from the MMRM models will be combined using the following code:

```

data diffdt;

  set midiffs;

  comparison=trt||' vs '||left(_trt);

run;

proc sort data=diffdt;

  by comparison shift;

run;

ods output parameterestimates=miparm1;

proc mianalyze data=diffdt alpha=0.05 theta0=0;

```

```

    by comparison shift;

    modeleffects estimate;

    stderr stderr;

run;

```

- Repeat steps 1 through 3 using the same values for the shift parameter for active arms but with a different positive value for placebo group. For example, SAS code below indicated a shift of 2 for placebo group.

```

mnar adjust( wk1 / shift=2   adjustobs=(trt='D' ) );
mnar adjust( wk2 / shift=2   adjustobs=(trt='D' ) );
mnar adjust( wk3 / shift=2   adjustobs=(trt='D' ) );
mnar adjust( wk4 / shift=2   adjustobs=(trt='D' ) );
mnar adjust( wk5 / shift=2   adjustobs=(trt='D' ) );
mnar adjust( wk6 / shift=2   adjustobs=(trt='D' ) );
mnar adjust( wk7 / shift=2   adjustobs=(trt='D' ) );
mnar adjust( wk8 / shift=2   adjustobs=(trt='D' ) );
mnar adjust( wk9 / shift=2   adjustobs=(trt='D' ) );
mnar adjust( wk10 / shift=2  adjustobs=(trt='D' ) );
mnar adjust( wk11 / shift=2  adjustobs=(trt='D' ) );
mnar adjust( wk12 / shift=2  adjustobs=(trt='D' ) );

```

- Repeat step 6 with a few different positive values for placebo group.
- Steps 2 through 5 will be repeated using different values for the shift parameter. After this step,, a treatment effect (difference in adjusted means from placebo) and associated p-value will be estimated for each shift parameter.

Since the tipping point analysis is to find out how much of a change is required to “tip” the result from statistically significant to not statistically significant, it will not be performed for any comparison that is not statistically significant at the onset.

Change from Baseline in 1-hour Postdose Percent Predicted Morning FEV₁ at Week 12:

The 1-hour postdose percent predicted morning FEV₁ measurement will be performed at the investigational center at the RV, TV2 (week 1), TV3 (week 2), TV4 (week 4), TV5 (week 8) and TV6 (week 12). MI method will be applied similarly to impute the 1-hour postdose missing data that are caused by early dropouts, then tipping point analysis will be performed.

APPENDIX D. SENSITIVITY ANALYSIS: MIXED APPROACH OF LOCF AND BOCF

With this approach, missing data caused by early dropouts from the study will be handled by two parts: a positive change from baseline score will be penalized by using the BOCF method. This will assign patient's change from baseline score to zero. Discontinued patient that has negative change from baseline with last nonmissing score (LOCF) will not have his/her result adjusted, since his/her score will be poor already.

Change from Baseline in Weekly Average of the Percent Predicted Trough Morning FEV₁ at Week 12:

The approach will be implemented as follows. Let C denote the change from baseline in percent predicted trough morning FEV₁, then

$$C = f_i - f_0 \quad [1]$$

where f_i is the last nonmissing FEV₁, and f_0 is the baseline of percent predicted FEV₁.

The primary analysis variable that accounts for early dropout, S , will be defined as follows:

$$S = \begin{cases} C, & \text{if } C \leq 0 \\ CP, & \text{if } C > 0 \end{cases} \quad [2]$$

where C is given by equation [1], $P=1$, if a patient completes the study by protocol or if a patient's final FEV₁ is measured at week 12, and $P=0$, otherwise. Note that retrieved dropout data will not be used for this analysis.

The primary analysis of change from baseline in weekly average of percent predicted trough morning FEV₁ at week 12 of S , as defined in equation [2] above, will be analyzed using an analysis of covariance (ANCOVA) model with effects due to baseline percent predicted trough morning FEV₁, sex, age, (pooled) investigational center, previous therapy (ICS or NCS), and treatment. Contrasts for pairwise treatment comparisons of interest will be constructed. The estimated treatment difference between each contrast of interest (i.e, Fp MDPI vs Placebo) will be presented together with the 2-sided 95% confidence interval (CI) for the difference and the p-value. The following SAS code pertains to the analysis:

```
proc mixed data=fev1cfb;
    class sex center therapy trt;
    model S=bfev sex age center therapy trt;

    /* Compare active Fp treatment to Placebo at Week 12 */
    estimate 'Fp 25 mcg BID vs Placebo'      trt  1 0 0 -1 /cl;
    estimate 'Fp 50 mcg BID vs Placebo'      trt  0 1 0 -1 /cl;
```

```
lsmeans trt / diff cl;  
ods output Estimates=Est LSMeans=lsmeans Diffs=Diffs;  
run;  
where: S is defined as in equation [2] above; bfev is the baseline  
value of FEV1; and trt is the treatment for the primary analysis:
```

```
A = Fp MDPI 50 mcg BID  
B = Fp MDPI 100 mcg BID  
C = FS MDPI 50/12.5 mcg BID  
D = Placebo
```

Change from Baseline in 1-hour Postdose Percent Predicted Morning FEV₁ at Week 12:

The 1-hour postdose percent predicted morning FEV₁ measurement will be performed at the investigational center at the RV, TV2 (week 1), TV3 (week 2), TV4 (week 4), TV5 (week 8) and TV6 (week 12). Mixed approach of LOCF and BOCF method will be applied similarly to impute the 1-hour postdose missing data that are caused by early dropouts from the study IMP.

APPENDIX E. SENSITIVITY ANALYSIS: MMRM

Similar to the primary estimand, retrieved dropout data will not be used in this sensitivity analysis. Missing data are not implicitly imputed in the MMRM analysis; however, all nonmissing data for a patient will be used within the analysis to estimate the time-averaged difference between treatment groups over 12 weeks. This analysis represents a MAR assumption.

Change from Baseline in Weekly Average of the Percent Predicted Trough Morning FEV₁ Over Week 12:

The sensitivity analysis will be performed using a MMRM with effects due to baseline FEV₁, sex, age, (pooled) center, previous therapy (ICS or NCS), week, treatment, and week-by-treatment interaction. No explicit structure will be assumed for the covariance among the repeated measures. However, if there is a convergence problem with unstructured covariance, then a compound symmetry covariance structure will be assumed.

The estimated treatment means and treatment mean difference derived from the MMRM analysis between each treatment will be presented together with 2-sided 95% CI for the means and the mean difference with corresponding p-value. An example of the SAS codes is as followed:

```
proc mixed data=fev1cfb;
    class usubjid sex center therapy week trt;
    model cfev=bfev sex age center therapy week trt week*trt
        /ddfm=KR;
    repeated week / type=un sub=usubjid(trt) r;
        ***repeated week / type=cs sub=usubjid(trt) r;
        ***If type=un fails to converge;

    /* Compare active Fp treatment to Placebo over 12 weeks */
    estimate `Fp 25 mcg BID vs Placebo'      trt  1 0 0 -1 /cl;
    estimate `Fp 50 mcg BID vs Placebo'      trt  0 1 0 -1 /cl;

    lsmeans trt week*trt / diff cl;
    ods output Estimates=Est LSMeans=lsmeans Diffs=Diffs;

run;
where: cfev and bfev denote change from baseline and baseline value of
percent predicted FEV1 respectively; week = 1, 2, 3, 4, 5, 6, 7, 8, 9,
10, 11, 12 representing weeks 1 to 12 respectively; and trt is the
treatment for the primary analysis:

    A = Fp MDPI 25 mcg BID
    B = Fp MDPI 50 mcg BID
```

C = FS MDPI 50/12.5 mcg BID
D = Placebo

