6.2. Primary Estimands and Efficacy Analyses

The estimands selected for the 2 primary endpoints will assess the change from baseline due to the initially randomized treatment as actually taken. These estimands assess the effectiveness at week 12, focusing on the causal effects attributable to the initially randomized medication. The sponsor will make all efforts to avoid study withdrawal in this 12-week study. In instances where a patient decides to discontinue IMP or, more importantly, requires alternative therapy for worsening asthma or an asthma exacerbation, the investigators will be instructed to encourage the patient to continue in the study and return for planned visits until the study completion in order to collect data after IMP discontinuation.

The question of whether to use data collected after IMP discontinuation is an ongoing debate in statistical literature, in particular for studies with symptomatic endpoints and when it is common for patients who dropout to switch therapies ([Mallinckrodt et al 2016](#), [Mallinckrodt 2013](#), [Little and Kang 2015](#), [O'Neill and Temple 2012](#)). This study is designed as a placebo-controlled study and it is expected that patients randomized to placebo would discontinue IMP due to worsening asthma at a higher rate than those randomized to active treatment, which is known to be an efficacious drug as established by multiple studies. After a patient discontinues IMP due to worsening asthma, the patient will be placed on alternative asthma therapies. The first choice will be ICS or a combination of ICS/LABA, exactly the classes of drugs being studied. Other therapeutic choices will include systemic corticosteroids, additional medications other than ICS, or both. All alternatives are proven to alter the spirometry collected after that point and therefore not be appropriate for assessment of IMP effectiveness. Improvement of asthma would be expected as rapidly and early as 1 week for FEV₁ for placebo patients placed on ICS ([Szeffler et al 1999](#)). It has also been shown that patients placed on ICS with long acting beta-agonists can have significant improvement in serial FEV₁ measurements on the same day ([Corren et al 2007](#), [Pearlman et al 1999](#)). Therefore, any patient who discontinued IMP and was placed on alternative therapies would be expected to have rapid and demonstrable improvements in lung function approximating the levels measured at screening.

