6.2.2. Primary Efficacy Analysis

6.2.2.1. For Fp MDPI versus Placebo: Change from Baseline in Weekly Average of the Percent Predicted Trough Morning FEV₁ at Week 12

For the purpose of the efficacy analysis of weekly average of daily morning FEV₁ measurements, the FEV₁ value at week 12 will be the average based on the available data for that week. The averages will be calculated as the sum of the morning FEV₁ values divided by the number of nonmissing assessments. There will be no imputation applied to postrandomization daily assessments.

The primary analysis of the change from baseline in weekly average of percent predicted morning FEV₁ at week 12 due to the initially randomized treatment as actually taken will be analyzed using an ANCOVA model with effects due to baseline percent predicted trough

morning FEV₁, sex, age, (pooled) investigational center, previous therapy (ICS or NCS), and IMP treatment group. Contrasts for pairwise treatment comparisons of interest will be constructed. The estimated treatment difference between each IMP treatment group and the placebo group will be presented together with the 2-sided 95% CI for the difference and the p-value.

In this analysis, missing data that are caused by early dropouts from the study or from IMP (regardless of availability of retrieved dropout data) will be imputed using reference-based multiple imputations which represents a missing not at random (MNAR) mechanism. The reference-based multiple imputation method multiply imputes the missing data in treatment group based on an imputation model built using data from the placebo group. This will yield a conservative treatment effect estimate as compared to the estimate obtained from multiple imputations (MI) under a missing at random (MAR) mechanism. The methodology and algorithm used for imputation is described in [Appendix A](#).

6.2.2.2. For FS MDPI versus Fp MDPI: Change from Baseline in 1-hour Postdose Percent Predicted Morning FEV₁ at Week 12

The baseline predose percent predicted trough morning FEV₁ will be performed at the **investigational center** at the RV (TV1) (Section 4.2 for details). The postdose percent predicted morning FEV₁ (measured at the investigational center) at week 12 with the handheld device will be approximately 1-hour after the IMP administration.

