6.2.2.3. Sensitivity Analyses

The following list of sensitivity analyses are prespecified for this study, to evaluate alternative estimands and assess the robustness of the primary efficacy results. Each sensitivity analysis will be conducted for the 2 primary efficacy endpoints, unless otherwise noted.

- Effectiveness with retrieved dropout data: to evaluate the estimand of the effect of the treatment regimens as actually taken (effectiveness), the analysis will be repeated including observed FEV₁ data over 12 weeks, for patients who completed the 12-week treatment period and for patients who discontinued from treatment earlier than week 12 but from whom the sponsor was able to collect efficacy data post discontinuation. Early withdrawal patients for whom the sponsor fails to retrieve data post discontinuation despite all attempts to contact the patient, a reference-based

imputation (RBI), which is an MNAR mechanism, will be utilized. The RBI method multiply imputes the missing data in every treatment group based on an imputation model built using data from the placebo group. This will yield a conservative treatment effect estimate as compared to the estimate obtained from multiple imputations (MI) under MAR (see [Appendix A](#) for details).

- **Treatment completer analysis:** In this completer analysis, the estimand is conditional on taking IMP. This estimand applies to all patients in the ITT analysis set who have completed the 12-week treatment period; patients who have taken their medication as directed without any major protocol violations. Note that since the use of incorrect IMP is considered a major treatment administration protocol violation, “as randomized” will coincide with “as treated” for the treatment assignment in this population. No imputation will be used since this is a completer analysis.

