- MMRM: similar to the primary estimand (change due to the initially randomized treatments as actually taken without retrieved dropout data), this sensitivity analysis will be performed using a MMRM model. This analysis represents a MAR assumption. The sensitivity analysis will be performed for the first primary endpoint, ie, change from baseline in the weekly average of percent predicted trough morning FEV₁ over the 12-week treatment period. Details are provided in [Appendix E](#).

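### The MMRM check on the trough endpoint reports a 12-week average, so it changes the time point together with the missing-data assumption; the week-12 MMRM difference should be named as the MAR result

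*SAP*

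**What the plan says.** The primary trough comparison is fixed at week 12. SAP 6.2 says of the primary estimands: "These estimands assess the effectiveness at week 12, focusing on the causal effects attributable to the initially randomized medication". SAP 6.2.2.1 says that the change from baseline "at week 12 due to the initially randomized treatment as actually taken will be analyzed using an ANCOVA model". Data missing after dropout or IMP discontinuation are filled by reference-based multiple imputation from the placebo group, which the SAP calls MNAR.

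The MMRM is one of the sensitivity analyses in SAP 6.2.2.3, whose stated purpose is "to evaluate alternative estimands and assess the robustness of the primary efficacy results". In the protocol it stands in Section 9.5.4.2, which is devoted to sensitivity to missing data. It excludes retrieved dropout data and assumes MAR. Its endpoint is "change from baseline in the weekly average of percent predicted trough morning FEV₁ over the 12-week treatment period".

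Appendix E makes the target explicit: "all nonmissing data for a patient will be used within the analysis to estimate the time-averaged difference between treatment groups over 12 weeks". In the SAS code, the comment "Compare active Fp treatment to Placebo over 12 weeks" stands above two ESTIMATE statements on treatment alone, one for each Fp dose against placebo. The code also contains "lsmeans trt week*trt / diff cl", which prints treatment differences week by week, week 12 included. No sentence says that the week-12 row is the sensitivity result.

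**The concern.** A check on missing data is readable when it keeps the question fixed and changes only the assumption about what is missing. Here two things change: reference-based MNAR becomes MAR, and the week-12 difference becomes an average over weeks 1 to 12. If the MMRM agrees with the primary result, the averaging may be the reason. If it disagrees, an effect that builds slowly may be the reason.

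No other analysis supplies the missing comparison. The retrieved-dropout, completer and LOCF/BOCF analyses stay at week 12 but are not MAR analyses. The tipping-point analyses start from MAR (shift zero), but they run only after a significant primary result. Their code also fits an MMRM and prints treatment-level LS means only, which again average over visits. So no MAR analysis of this endpoint declares a week-12 difference as its result.

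**Working it through.** **1. The plan's own figure.** SAP 2.4 gives SD 17, a figure of 5, 80% power, two-sided 0.05, 181 per arm, 12% dropout and 206 randomized per arm.

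- n = 2 × 17² × (1.960 + 0.842)² / 5² = 181.5, which rounds up to 182 against the stated 181. Power at 181 is 79.9%.
- 181 / 0.88 = 205.7, so 206.

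The figure of 5 is worded as an overall mean change, but 181 comes out only if it is used as the between-arm difference. I use it that way.

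**2. What the ESTIMATE statements compute.** The model contains the week-by-treatment interaction. A contrast on treatment alone (`trt 1 0 0 -1`) then weights each of the 12 weekly differences by 1/12. Week 12 carries 1/12 of the result; weeks 1 to 11 carry 11/12.

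**3. Precision of the two contrasts.** The documents give neither a between-week correlation (ρ) nor the timing of dropout. I assume compound symmetry with ρ = 0.4, 0.6 or 0.8, and 12% dropout spread evenly, so that w% are missing at week w. With complete data the SD of the 12-week average is 17 × √((1 + 11ρ)/12), that is 11.40, 13.53 or 15.36. With dropout I summed the information over dropout patterns for the 12 weekly means of one arm, inverted it, and multiplied the standard errors by √2 for a two-arm difference.

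| ρ | SE, week 12 | SE, 12-week average | Reduction |
|---|---|---|---|
| 0.4 | 1.76 | 1.14 | 35% |
| 0.6 | 1.73 | 1.35 | 22% |
| 0.8 | 1.71 | 1.53 | 11% |

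Mean missingness over the 12 weeks is 12% × 6.5/12 = 6.5%, against 12% at week 12. This ratio depends on the even-dropout assumption.

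**4. Three illustrative effect profiles.** Probability of two-sided significance at 0.05, normal approximation, for ρ = 0.4 / 0.6 / 0.8:

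| Profile | Mean over 12 weeks | 12-week average | Week-12 contrast |
|---|---|---|---|
| Constant 5 | 5.00 | 99% / 96% / 91% | 81% / 82% / 83% |
| 5 to week 6, then linear to 0 at week 12 | (30 + 12.5)/12 = 3.54 | 87% / 75% / 64% | 5% (2.5% in favour of Fp) |
| Linear build, 5w/12 | 5 × 6.5/12 = 2.71 | 66% / 52% / 43% | 81% / 82% / 83% |

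With a constant effect the two contrasts estimate the same value and differ only in precision. With a fading effect the average can look sound when week 12 is not. With a slow build it can look weak when week 12 is sound.

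**The case against.** The strongest reply is that this is a declared choice. The protocol synopsis, Protocol 9.5.4.2, SAP 6.2.2.3 and Appendix E all place the MMRM over the 12-week period, and SAP 6.2.2.3 allows for alternative estimands. That stands: protocol and SAP do not contradict each other. But the same sentence names robustness of the primary results as a purpose, and this contrast cannot isolate that.

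A reader might infer that the SAP presents the MMRM as matching the primary estimand, because the 6.2.2.3 bullet calls it similar. The bullet's own parenthesis ties the similarity to treatment as actually taken without retrieved dropout data. It says nothing about the time point.

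A reader might also infer that the MMRM could carry a claim when the week-12 effect is gone, and take 87% / 75% / 64% as the chance of that. The documents do not support this. The MMRM is outside the fixed testing sequence (Protocol 9.6, SAP 7.1). With no true week-12 effect, the primary test favours Fp only about 2.5% of the time, so a positive result wrongly supported by the MMRM can arise no more often than that. The percentages are unconditional rejection rates of the average contrast.

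Nor do early weeks dominate: the weights are equal, and weeks 1 to 6 carry exactly half.

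It is also true that the effect profiles are invented for illustration. SAP 6.2 expects FEV₁ to improve within about a week of starting ICS, which lies closer to the constant case. Compound symmetry is only the SAP's fallback to an unstructured covariance. Finally, the week-12 MMRM difference will be printed anyway, so what is missing is its designation.

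**Conclusion.** The point holds as a mismatch between a sensitivity analysis and the estimand that it is meant to test. It is neither an error in the primary analysis nor a threat to the type I error rate. That two things change at once follows from the text and needs no assumption. The size does rest on assumptions: a standard error 11% to 35% smaller for ρ from 0.8 to 0.4, with SD 17, 206 per arm and 12% evenly spread dropout. Any divergence in the estimates themselves depends on an effect profile that the documents do not give. This is a cheap improvement: a better target for an analysis already planned, taken from output already requested.

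**What to change.** In SAP Appendix E, the MMRM bullet of SAP 6.2.2.3 and Protocol 9.5.4.2 (with the matching synopsis bullet), name the week-12 differences from the MMRM, Fp 50 mcg versus placebo and Fp 25 mcg versus placebo, with 95% CI and p-value, as the MAR sensitivity result. They can be taken from the week-by-treatment LS means already requested, or from added week-12 ESTIMATE or LSMESTIMATE statements. Keep the 12-week average as a separately labelled supportive summary. If only the SAP is changed, add an entry to SAP Section 11, which at present declares no change to the protocol's analyses apart from a clarification of the per-protocol set.

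The cost is a few lines of text and code and no new data. The reported MMRM interval will be somewhat wider than that of the average.
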